## LIST OF ABBREVIATIONS

ALT	Alanate Aminotransferase
AST	Aspartate Aminotransferase
AUDIT	Alcohol Use Disorder Identification Test
BCG	Bacillus Calmette-Guérin
CEP	Research ethics committee
DNA	Deoxyribonucleic Acid
AE	Adverse Event
SAE	Serious advers event
HIV	Human Immunodeficiency Virus
INH	Isoniazid
IGRA	Interferon gamma reelease assay
LPCS/UFGD	Research Laboratory in Health Sciences/Federal university of Grande Dourados
MDR	Multidrug-resistant
MS	Ministry of Health
Mtb	Mycobacterium tuberculosis
WHO	World Health Organization
PED	State Penitentiary of Dourados
SOP	Standard Operational Procedure
PPD	Purified Protein Derivative
TB	Tuberculosis
TCLE	Informed consent form
DOT	Directly Observed Treatment
UEMS	State University of Mato Grosso do Sul
XDR	Extensively Drug-resistant

## 1 INTRODUCTION

Despite being a disease known to humanity for more than 9,000 years ago, tuberculosis (TB) still represents a serious public health problem in developing countries.

TB is an infectious, airborne disease that can present in both active and latent forms. Despite the biological aspect of transmission, unhealthy environmental conditions (eg, environment without direct sunlight, poor ventilation, overcrowding, etc.) and individual factors (malnutrition, immunosuppression, use of alcohol, other drugs, etc.) have a significant influence on the transmissibility and infectivity of the disease.

With the discovery of active drugs against *Mycobacterium tuberculosis*, a reduction in the incidence of the disease was seen worldwide. Despite this decreasing incidence, the World Health Organization (WHO) classified TB as a global public health problem, due to the appearance of multidrug resistant or extensively resistant tuberculosis disease, resistant to treatment. In addition reactivation of latent TB was consistently observed with the advent of HIV.

Several studies have shown a direct relationship between the incidence of TB and the prison environment. The presence of prison units in a locality raises the incidence of the disease, suggesting tuberculosis transmission between the prison and the community.

To date, TB control in prisons is based on screening individuals with active and/or latent TB and their treatment. To identify individuals with active disease, diagnostic algorithms using respiratory symptoms (mainly cough), sputum culture, and chest radiography are used. Regarding the search of individuals with latent tuberculosis, the skin test with the PPD can be performed.

Prisoners in Brazil have short incarceration terms, usually leaving prison within one to two years. Therefore, an intervention that protects prisoners from acquiring recent infection during prison stay may be adequate for long-term tuberculosis control in these prisons. Although there is a large body of empirical evidence demonstrating that isoniazid prevents progression to active tuberculosis, whether isoniazid prevents primary infection is unknown.

The aim of this study was to determine the efficacy of primary prophylaxis in the prison population in order to gather new scientific evidence that would bring accessible methods for the control of TB in prisons.

## 2 BACKGROUND

### 2.1 *Mycobacterium tuberculosis*

*M. tuberculosis* was discovered by Robert Koch in 1882. It is an immobile, aerobic bacterium of the *Mycobacterium tuberculosis* complex. This complex is formed by several species of mycobacteria, causal agents of TB in different hosts: *M. tuberculosis*, *M. africanum*, *M. canetti* (affect humans); *M. microti* (infect mice); *M. bovis* (affect cattle); *M. pinnipedi* (found in seals and sea lions); *M. caprae* (infect sheep and goats) and BCG vaccine strain(1). Different bacterial strains of the *M. tuberculosis* complex are closely related, with 99.9% genetic similarity and strong host specificity(2,3).

*M. tuberculosis* is primarily responsible for most TB cases in humans. The main characteristics of *M. tuberculosis* are the high content of guanine-cytosine in its DNA; the long generation time (cell division between 12 to 24 hours under favorable conditions) and the special cell wall, shared by all species of the Mtb complex. The structure of this wall is its composition: highly cross-linked peptideoglycans and mycolic acid, making the bacterium highly hydrophobic and acid-resistant, a characteristic that is used to diagnose the disease(4,5). The lipid-rich cell wall forms the basis for the intrinsic resistance of Mtb to most antibiotics(6).

TB is transmitted primarily through aerosols. Aerosols are tiny droplets containing bacteria, formed when a patient with active TB coughs or sneezes. If these droplets are inhaled by another susceptible person (or animal), the bacteria enter the lung where they are phagocytosed by the macrophages. In other words, Mtb must be active to be transmitted. A person with active TB can infect an average of 10 to 15 people within a year(7). However, the amount of bacilli present, its virulence, health status (co-infections, immunosuppression), the individual's age, and adequate environmental factors such as ventilation and exposure to sunlight (ultraviolet light) have a great influence on infectivity. Yet, theoretically, TB is infectious for a long time while bacteria are viable in the sputum. If a patient is under treatment, it takes about 4 to 8 weeks until no more bacteria are detected in his sputum(4). As the first organ affected is the lung, most cases of TB are called pulmonary TB. Even so, TB can affect other parts of the body, in this case called extrapulmonary TB. In these occasions, the individual is usually not infectious, since the bacterium is not expelled through the aerosols, however, may present clinical of the disease.

Once the bacteria entered the lung they are phagocytosed by alveolar macrophages. Mtb can grow within macrophages by inhibiting the fusion of phagosomes with lysosomes, thus avoiding their digestion. Granulomas are formed - aggregation of infected phagocytes (macrophages, neutrophils, monocytes and dendritic cells) and surrounded by B and T lymphocytes(8). At first three scenarios are possible: first, the immune system overcomes bacteria, which are killed and eliminated completely; Second, bacteria outgrow the immune system and multiply in the lung, causing disease; Third, there is a balance between the bacteria and the immune system, which are in a dormant state called latent TB. When the individual has latent TB, the infection remains clinically silent and the bacteria do not spread. In 90-95% of cases the bacteria remain dormant and never reactivate. In the remaining 5-10% reactivation of bacteria occurs after a few years, leading to clinical disease, called secondary TB(9).

The hypotheses described above must be seen as a result of a dynamic transmission system, in which the course depends on both host and bacterial factors(10). One reason for the reactivation of latent TB is HIV co-infection. CD4 lymphocytes play a key role in the formation of granulomas, as they produce cytokines (eg, IL-12 and IFN- $\gamma$ ) that activate macrophages. CD4 lymphocyte count is generally low with the advancement of HIV infection, patients living with HIV are at high risk (over 40 times) of becoming infected with TB and progressing to TB(11,12).

The most common symptom of TB is productive and persistent cough for several weeks, thus serving as an indicator for TB screening in endemic countries. It is often accompanied by other nonspecific symptoms such as fatigue, fever, night sweats and later weight loss, chest pain and difficulty breathing(7).

## **2.2 Epidemiology**

TB and humans have coexisted for a long time. Estimates suggest that this relationship occurs at least 70,000 years(13). Physical evidence of bacteria in humans has been found in two 9,000-year-old bodies from Haifa, Israel, and from Egyptian mummies dating from 1550 to 1080 BC(14,15). However, TB only appeared epidemic in Europe and North America in the 18th and 19th centuries, declining with the introduction of isolation and chemoprophylaxis and reemerging again in the 1980s and early 1990s as a result of the HIV pandemic and increased resistance to drugs used in treatment(16,17).

In 1993, WHO declared TB a global emergency, given the rise in multi-drug resistant cases and the HIV epidemic(18). As a consequence, the DOT strategy was developed and, after a few years, the STOP TB Strategy was formed, a network of public and private organizations from several countries, with the participation of governments and collaborators, whose purpose is to reduce drastically the burden of disease worldwide(19,20).

TB remains the leading global health problem today. One third of the global population is infected and 8.6 million people developed the disease, resulting in 1.3 million deaths in 2012(7). Most TB cases are found in Southeast Asia (29%), Africa (27%) and Western Pacific Region (19%). The 22 countries with the highest burden of disease represent 82% of the reported cases in the world, with India and China alone representing 39% of this. TB affects more men than women and yet causes one in three deaths in this population, especially those living with HIV. All age groups are affected by the disease, but most cases occur in the economically active population. TB in children has been neglected for a long time, since they do not represent the most infectious cases. However, children are an indicator for active transmission and in 2012 accounted for 6% of the total cases detected(7).

To reduce the global burden of TB, the STOP TB Strategy formulated several targets to be achieved by 2015, in line with the Millennium Development Goals(21). Although the overall mortality rate has dropped by 45 per cent and the prevalence by 37 per cent since 1990, several of the targets proposed, for example the goal of reducing the prevalence of active TB by 50 per cent, have probably not been met by 2015, especially in Africa and European region formed by the countries of the Soviet Union, where mortality and prevalence remain high(22). Large numbers of people with latent infection, HIV pandemic and increased bacterial resistance challenge the achievement of targets to eliminate TB as a public health problem by 2050. Every year about 450,000 new cases of MDR are detected, with the estimated global rate of 9.6% in new cases and 92 countries have reported at least one case of XDR TB so far (7,23). Less than 25% of estimated MDR TB cases worldwide are detected and only 50% of cases initiating therapy are successfully treated.

## **2.3 The relation prison and tuberculosis**

The world prison population is currently estimated at 10.2 million people(24). Brazil has the third largest population in the world, with 688,759 individuals in 1,449 establishments, and the incidence of TB in this population has increased in the last seven years(25). Although prisoners represent only 0.3% of the country's population, an increase in the prison population over this period has resulted in almost double the proportion of all TB cases among prisoners (4.1% in 2007, 8% 1% in 2013).

The prison environment contributes greatly to the transmission of TB. Prisons are an ideal environment for the transmission of the disease, since they bring together individuals who use tobacco and alcohol in high doses, in addition to drug abuse, in overcrowded cells, with little ventilation and with limited access to care. health and diagnosis of TB. Urrego et al.(26) collected architectural and ventilation data in a southern prison in Mato Grosso do Sul and, using a modified Wells-Riley model for indoor TB transmission, projected TB transmission rates within each cell , provided that an infectious case was present. They estimated that 53-70% of cell mates would be infected after four months of exposure.

In a case-control study associated with molecular methods, Sacchi and cols.(27) examined the role of prison in TB burden in the population of Dourados. Among 240 cases of TB reported over a 46-month period, 180 (75%) occurred in the general population and 60 (25%) in the prison population, showing a 40-fold increased risk (incidence) among prisoners of TB. Among the TB cases of the general population, 23% occurred among residents who were previously incarcerated. Previous incarceration was the strongest risk factor for TB in the community (adjusted OR, 28.5). Among 97 isolates for which restriction fragment polymorphism (IS6110) genotyping was performed, 79 could be classified into 17 groups. Ten of these 17 sets, comprising 82% of the clustered isolates, involved two prisoners and community members, including the former detainees. These results demonstrate a high degree of linkage between lineages in prisons and in the community; and indicate that the approach to TB transmission in prisons will be critical to disease control among the general population.

Carbone et al.(28) carried out a cross-sectional study to estimate the prevalence of active and latent TB and associated risk factors among 3,380 prisoners (2,861 men, 519 women) from the 12 penitentiaries in Mato Grosso do Sul. The prevalence of active TB was calculated as 917 cases per 100,000 inmates and the latent one, at 21%. Comparing the prevalence and annual reports of TB, the mean infection time was estimated at 4.8 months.

## **2.4 Prophylactic use of isoniazid**

The discovery of INH was based on the activity of nicotinamide against TB bacilli in an animal model, observed by Chorine in 1945, and the rearrangement of chemical groups in thiosemicarbazone. INH represents an important milestone in TB chemotherapy because it is highly active against bacilli, low cost and without significant side effects.

In 1952 it was proved that the drug had tuberculostatic activity, however, the target of action was unknown(29,30). Subsequently, it has been found that INH inhibits the synthesis of mycolic acids,  $\alpha$ -alkyl  $\beta$ -hydroxy and higher chain fatty acids that cover the surface of the mycobacteria. The main molecular target of action of INH is the *inhA* gene, which encodes the enzyme *inhA*. This enzyme catalyzes the transfer of a hydrogen atom to the substrate at its catalytic site using NADH, which is a reducing agent found in numerous biochemical processes in living beings as a source of hydrogen(31).

Due to the bacterial resistance to streptomycin (discovered in the previous decade) the use of INH in the treatment of TB started successfully. Although it was generally well tolerated by patients, cases progressing with pruritus and hepatitis were recorded(32). Salpeter(33), in a review covering 20,212 individuals who started chemoprophylaxis with INH, estimated the incidence of hepatitis at 1%, with 8,700 individuals being 35 years of age or older.

In 1963 Hanson, Comstock, and Haley(34) conducted a community-based clinical trial in Alaska using chemoprophylaxis with INH in half a population (about 9,000 subjects) who received a daily dose of the drug (5mg / kg) for 12 months. The intervention was performed based on the epidemiological picture of the region, whose TB incidence was 20 times higher than the North

American population, in addition to conditions considered propitious for transmission (small, overcrowded, poorly ventilated and malnourished individuals). The results showed the occurrence of 32 cases of TB in the control group, compared to 1 case in the treatment.

The conditions described by Hanson, Comstock and Haley in the Alaskan population are similar to those currently found in the prison system in developing countries. However, in this review, no studies were found on the prophylactic use of INH in prisons, and its use was restricted to cases of latent TB.

## **2.5 Isoniazid in the treatment of latent TB**

In 1999, Smieja et al.(35), in a review to identify the efficacy of INH in non-HIV subjects, found that the relative risk of acquiring TB after 6 months of prophylaxis with 300mg of the drug was 0.40 (95% CI 0.31 -0.52), with an absolute risk reduction of 0.01, ie, it would take 100 treatments to avoid 1 case of active TB. The most frequent adverse reactions were mild and transient headache, nausea, dizziness. The occurrence of hepatitis was 0.12% in the controls and 0.52% in the treatments, having as risk factors age greater than 45 years and alcohol use.

Sharma et al.(36) in a review comparing regimens with rifamycin (and its derivatives, including rifapentine) and INH, conclude that regimens using rifamycin alone are longer, have a lower completion rate, and do not present advantages over the INH regimen alone.

Epidemiological conditions conducive to high TB transmission are currently found in the prison system (26). Macintyre et al.(37) conducted a cohort study in 16 of the 23 prisons in Maryland and concluded that the use of INH prophylaxis reduced the risk of progression to active TB in individuals reacting to the skin test by 50%. Al-Darraj; Kamarulzaman and Altice(38) have shown, through a systematic review covering 18 publications (between cohort and transverse studies) that the efficacy in cases of latent TB is about 60% in non-HIV individuals and 36% in individuals with HIV, using INH for 6 months. The hepatotoxicity rate was on average 6%. Approximately two-thirds of these studies were conducted in countries with low endemicity for the disease. In view of this, the authors recommend that further studies should be conducted, but in countries highly endemic for the disease, to explore the efficacy and safety of INH in closed prisoners.

Two randomized clinical trials showed an 83.8% and 69% adherence rate with an isolated INH regimen and a hepatotoxicity of 2.4% and 2.7%(39,40). It is noteworthy that in the aforementioned studies all the individuals allocated in the treatment group had latent TB diagnosed through the skin test with PPD.

### 3 RATIONALE

Despite advances in TB diagnosis and treatment, it is the third leading cause of death from infectious diseases in the world(41). In 2015, WHO estimated that 9.6 million new TB cases worldwide occur, with about 1.1 million deaths. For Brazil, the incidence of 44 cases per 100,000 inhabitants(42) was estimated. The incidence of TB has decreased by around 2% per year.

Brazil occupies the 22nd place in the WHO ranking with an annual rate estimated in 83,310 cases of the disease (42). Over the past seven years, it has been estimated that the incidence declined only 0.7% (per year). A key factor in this slow progress in TB control in Brazil and in other emerging countries is the existence of high-risk subpopulations, including favelas and prisons, which serve as reservoirs and amplifiers for the transmission of the disease(43,44). A recent systematic review has shown that the average incidence of TB in the prison population may be up to 23 times that recorded in the general population(45).

With the third largest population of prisoners in the world, the increase in the incidence of TB among prisoners in the last seven years is observed in Brazil. Although prisoners represent only 0.3% of the country's population, an increase in the prison population over this period has resulted in almost double the proportion of all TB cases among prisoners (4.1% in 2007, 8% 1% in 2013).

Prisons are an ideal environment for TB transmission, since they bring together high-dose tobacco and alcohol users, as well as drug abuse, in overcrowded, poorly ventilated, and limited access health and diagnosis of TB. Currently, the Ministry of Health recommends the active search for TB at the entrance to the prison and once a year, through the chest X-ray. Due to cost and logistics, most prisons do not adhere to this recommendation. There is also a clear recommendation not to use the tuberculin test or to perform treatment for latent TB. Whether procedures for active case detection and / or prophylactic treatment would impact on the high transmission of the disease in prisons is an issue that remains open(38).

The concentration of TB cases in prisons may represent both an obstacle and an opportunity for disease control, depending on the effectiveness of the interventions performed in these settings.

Preliminary studies show a high annual rate of TB infection (26%) among the prison population of 12 penitentiaries in Mato Grosso do Sul. In addition to the large burden of disease in this population, the dispersion of TB from prisons to the community is significant(27). Cross-sectional studies show a high yield of annual screening for TB, however, the effectiveness of this measure associated with other interventions has not yet been clarified(46–52). Because of the combination of the high force of infection in prisons and the short period of incarceration, primary prophylaxis can be an effective intervention.

This approach has not yet been evaluated in the context of prisons in middle- and low-income countries. Thus, in order to assess the impact of program strategies for TB control and primary prophylaxis, longitudinal data will be essential. Given the infrastructure that has been created for prospective long-term studies in Brazil, there is an excellent opportunity to close the fundamental knowledge gaps that have been barriers to effective implementation of TB control in high-transmission prisons.

## **4 AIMS**

### **4.1 General**

To determine the efficacy of primary prophylaxis with INH 900mg twice weekly in inmates in a closed regimen.

### **4.2 Specifics**

- Determine the impact of INH use on the incidence of active and latent TB in the prison population;
- To quantify the occurrence of adverse events, including hepatotoxicity, due to the use of INH;
- Evaluate residual protective effect until the 12th month after intervention;

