## **5 OUTCOMES**

### **5.1 Primary outcome**

Reduction of 50% in latent TB in the treatment group after 12 months of intervention, estimated by IGRA QuantiFERON TB Gold Plus – Qiagen.

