#### 6.1.1 Sample and population of the study

This research will be carried out at one prison unit, located in the city of Dourados, in the state of Mato Grosso do Sul. Currently, this prison unit has approximately 2,300 inmates, with a mean age of  $31.5 \pm 9.4$  years; an average of  $9.7 (\pm 4.2)$  individuals per cell, who remain in a closed regimen, about  $20.8 (\pm 24.1)$  months. The TB indicators show a tuberculin test seroconversion rate of 26% (23-26) and incidence, 2.45 / 100,000(28).

The sample was calculated for a significance level of 5%, detection power of 90%, considering a percentage of occurrence of latent TB of 20% in the control group after one year of follow-up and 10% in the experimental group. For these parameters, 560 individuals will be needed for the study, however, 30% will be added for possible losses, ending the sample in 728 participants. Memory calculation available at <https://www.sealedenvelope.com/power/binary-superiority/>.

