## 6.5 Conducting the study

Participants will be invited to participate in the clinical trial through the consent process and will agree to participate in the study by signing the ICF.

In the recruitment interval, prior to any intervention, participants will respond to the AUDIT questionnaire - which assesses various levels of alcohol use, from safe use to likely dependence - and eligibility criteria will be checked. In the recruitment interval, participants will have a 9mL sample of peripheral blood collected for testing of IGRA (QuantiFERON® TB GOLD PLUS kit - Qiagen, HIV, hepatitis B (HBsAg) and C (Anti-HCV) and serum levels of liver enzymes (AST and ALT).

After the results of these initial tests (HIV, hepatitis B and C, IGRA, AST and ALT), if eligible, the participant will answer questionnaires containing socioeconomic, medical and criminal history and have a sample of sputum collected for culture.

The participant will be included in the study without the result of the culture and, in case of a positive result for Mtb, the intervention will be suspended, the same will be excluded from the study and treated according to the MS protocol. If the sputum culture is contaminated, a new sample should be collected within 30 days after the result.

The recruitment interval will last 20 to 45 days.

On the day of initiation of DOT (D0), each participant will receive a supervised dose (three oral tablets) of INH (900mg) or placebo. The same will happen twice a week for 12 months. During the DOT the participant will be asked about AE.

Blood samples will be collected every three months after D0 to measure hepatic enzyme levels (AST and ALT), as well as clinical evaluation and verification of AE, as shown in figure 1.

At six months and at the end of the intervention (12th month), all participants will have a sample of sputum collected for culture and a blood sample for detection / quantification of interferon gamma. The same evaluation will be repeated in the 24th month counted from D0, that is, one year after the end of the intervention.

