## 6.6 Estatistical analysis

Data on demographic, socioeconomic, medical and criminal history, as well as on pre, intra and post-intervention laboratory tests will be stored online at REDCap, available at <<http://www.matogrossodosul.fiocruz.br/redcap/>>, where each researcher is identified by single user and password, guaranteeing restricted and confidential access. Statistical analysis will be done with IBM® SPSS Statistics software.

The incidence will be calculated on the basis of the new cases detected during the follow-up period, per 100 person-years. It will be considered a new case of TB individuals, regardless of the group, who present bacilloscopy or positive culture. For latent TB, a seroconversion will be considered for individuals who exhibit interferon gamma levels above the upper limit considered by the manufacturer of the QuantiFERON® TB Gold Plus commercial test in the 12th or 24th month.

The effect of the intervention will be calculated through Relative Risk (RR), considering a Confidence Interval of 95% (95% CI). To determine the effectiveness of the intervention will be used Relative Risk Reduction (RRR) and Absolute Risk Reduction (RAR). In addition, to measure the impact of the intervention, the Number Needed to Treat (NNT) will be calculated.

Two protocols will be performed for statistical analysis: 1) intention-to-treat analysis and 2) per protocol. The sample calculation for the primary outcomes is based on intention-to-treat analysis.

The intent-to-treat analysis will be performed for all subjects who complete at least 6 months of treatment. The participant may decide to withdraw the consent in whole or in part. In the case of withdrawal of partial consent IGRA will be withdrawn at the 12th or 24th month and the participant will remain in the study according to the initial randomization.

Analysis by protocol will be performed only using the group of individuals who completed at least 80% of the predicted doses of the study.

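### The latent-TB outcome window is inconsistent (12 months in 5.1 and 6.1.1, month 12 or 24 in 6.6), and no analysis is specified for the residual-protection aim in 4.2

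*Combined protocol and SAP*

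**What the plan says.** All references are to the combined protocol and SAP.

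- **Aim (4.2).** The third specific aim is to "Evaluate residual protective effect until the 12th month after intervention".
- **Primary outcome (5.1).** "Reduction of 50% in latent TB in the treatment group after 12 months of intervention", measured by IGRA. Section 5 contains no outcome for the residual-protection aim.
- **Sample size (6.1.1).** The planning rates are "latent TB of 20% in the control group after one year of follow-up and 10% in the experimental group", so the sample size belongs to a one-year outcome.
- **Schedule (6.5).** Doses are given for 12 months, with IGRA at months 6 and 12. Then: "The same evaluation will be repeated in the 24th month counted from D0, that is, one year after the end of the intervention". A participant with a positive IGRA leaves the study.
- **Analysis (6.6).** This is the only place where seroconversion is defined for analysis. It requires a result above the manufacturer's limit on the "commercial test in the 12th or 24th month". Incidence covers the whole follow-up period. The RR, relative and absolute risk reductions and number needed to treat (NNT) carry no time point. No analysis is restricted to months 12 to 24.

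**The concern.** Protection while taking isoniazid (INH) and protection in the year after stopping are different questions, and section 4 asks both. Section 6.6 offers one conversion rule covering both periods and does not say which visit the RR refers to. Read literally, someone infected in the off-drug year counts the same as someone infected on drug.

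Two things are at stake.

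- **The main RR.** A month-12-or-24 RR depends on how much protection persists after dosing, which is the unknown that the third aim is meant to measure. It would understate the on-drug effect. A value below 1 could also be taken as lasting protection when the whole benefit arose in year 1.
- **The timing of the choice.** Section 6.1.3 opens the allocation at the end of the study to allow the analysis. If the window is not fixed before then, it could be chosen with results by arm in view.

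Follow-up adds to the problem. Section 6.1.1 gives a mean closed-regime stay of 20.8 (±24.1) months, and 6.4 lists release or transfer as grounds for withdrawal. Some participants may have a month-12 result and no month-24 result. An either-visit outcome would then combine people followed for one year and for two years in a single risk.

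**Working it through.** **Inputs from the plan (6.1.1):** 5% significance, 90% power, 20% vs 10% at one year, 560 participants before losses (280 per arm). Sidedness is not stated; two-sided is used here.

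**Assumptions, not in the plan:** 20% placebo risk in year 2, a year-2 RR (r) of 1, 0.75 or 0.50, all conversions detected and counted, and no losses.

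**1. The plan's own figure.** With mean risk 0.15, the uncorrected size per arm is

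n = [1.96 × √(2 × 0.15 × 0.85) + 1.282 × √(0.20 × 0.80 + 0.10 × 0.90)]² / 0.10² = 266, or 532 in total.

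With continuity correction it is 286 per arm, or 572 in total, which is 12/560 = 2.1% above the stated 560. One-sided versions give 430 to 474. The stated size is therefore close to a two-sided calculation on one-year rates. The plan then takes 560 × 1.3 = 728.

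**2. Power formula.** Power = Φ{[Δ − 1.96 × √(2p̄(1−p̄)/n)] / √([p₁(1−p₁) + p₂(1−p₂)]/n)}.

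For month 12 alone with n = 280: (0.10 − 1.96 × 0.0302)/0.0299 = 1.37, so power is about 91%.

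**3. Month 12 or 24 merged.**

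- Control: 0.20 + 0.80 × 0.20 = 0.36
- INH: 0.10 + 0.90 × 0.20 × r

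| Outcome | Control | INH | RR | NNT | Power, 280 per arm |
|---|---|---|---|---|---|
| Month 12 only | 20% | 10% | 0.50 | 10 | 91% |
| Merged, r = 1 (no residual effect) | 36% | 28% | 0.78 | 12.5 | 53% |
| Merged, r = 0.75 | 36% | 23.5% | 0.65 | 8 | 90% |
| Merged, r = 0.50 (full persistence) | 36% | 19% | 0.53 | 5.9 | 99.5% |

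For r = 1: (0.08 − 1.96 × 0.0394)/0.0393 = 0.07, so power is about 53%. Reaching 90% would need 713 per arm.

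**4. Sensitivity.**

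- With the 26% annual infection rate quoted in section 3, and INH halving it in year 1, the merged RR runs from 0.79 (r = 1, power 64%) to 0.54 (r = 0.50, power above 99%).
- With the 20% rate, half the off-drug exposure and no residual effect, the risks are 28% vs 19%: RR 0.68, power 71%.

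**5. Off-drug year read separately.** Those still negative at month 12 number 280 × 0.80 = 224 on placebo and 280 × 0.90 = 252 on INH. Power is about 87% for 20% vs 10% (r = 0.50) and about 30% for 20% vs 15% (r = 0.75), before losses.

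**The case against.** The strongest reply is that the primary time point is already fixed. Section 5.1 names 12 months and 6.1.1 sizes the trial on one-year risk. On this view, the 6.6 wording is only a case definition that lists IGRA visits; the same pair of visits is named again where 6.6 deals with partial withdrawal of consent. Section 6.6 does not say that the visits are pooled in one RR. Since anyone positive at month 12 leaves, new conversions at month 24 come essentially from month-12 negatives, so a by-visit reading would give the right groups.

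Much of this stands. A reader might infer that the primary RR will be diluted and that the residual effect can never be estimated. The documents support neither. Dilution occurs only if 6.6 overrides 5.1, and the month-24 samples are scheduled, so the residual analysis is unspecified rather than impossible. The 53% power belongs to the no-residual-effect case alone; at r = 0.75 power is about the same as at month 12, and at r = 0.50 it is higher. Nor are the merged figures the exact result of 6.6 as written, because conversions found at month 6 leave the study and fall outside its two named visits.

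The reply does not remove the conflict. Section 6.6 does not say by visit either, and nothing states that 5.1 takes precedence over the only analysis definition.

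**Conclusion.** The point holds as an inconsistency plus an omission. The plan has two windows for latent TB, 12 months in 5.1 and 6.1.1 and either visit in 6.6, and the third aim in 4.2 has no outcome or estimator.

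The numerical consequence is conditional on 6.6 being applied literally to the main RR, and on a year-2 rate that the documents do not give. Under the stated assumptions a true on-drug RR of 0.50 would be reported as anything from 0.53 to 0.78. It moves toward 1 in every scenario examined. Loss of power is material only when residual protection is weak or absent.

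A separate off-drug analysis is not a clean randomised comparison. Being negative at month 12 is affected by treatment. If INH works, the INH group at risk in year 2 keeps people whose placebo counterparts have already converted and left. The cumulative 24-month comparison avoids this, but on its own it cannot separate residual from on-drug effect. Both are needed.

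**What to change.** In 6.6, before the allocation is opened:

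1. State that the primary RR uses conversion up to and including the month-12 visit, counts conversions found at month 6, and excludes month-24 results. This aligns 6.6 with 5.1 and 6.1.1.
2. Report cumulative 24-month risk by randomised arm as a secondary comparison that keeps randomisation.
3. For the 4.2 aim, add an analysis by arm of conversion first detected at month 24 among participants IGRA-negative at month 12, with RR and 95% confidence interval. Label it as conditional on a post-randomisation state and therefore open to selection bias.

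Attach the time point to each RR, risk reduction and NNT.

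The cost is wording and one extra table; no new data are needed. The drawback is precision: before losses, the residual analysis has about 87% power for a year-2 RR of 0.50 but only about 30% for 0.75, so a wide interval should not be read as absence of residual protection.
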